## 8. GENERAL CONSIDERATIONS FOR DATA ANALYSES

Analysis datasets will be created according to CDISC/ADaM standards, and data will be listed and summarized according to GSK Integrated Data Standards Library (IDSL) reporting standards. Formatting for dates, times, and decimal places will follow GSK standards except where specified.

The currently supported versions of SAS, S-Plus software, and TSCG (for figures) will be used to perform all data analyses, generate tables, figures, and listings.

All data in the database will be presented in by-subject data listings.

All data up to the time of study completion or withdrawal from the study will be included in the analysis, regardless of duration of treatment.

As the duration of treatment for a given subject will depend on efficacy and tolerability, the duration of follow-up will vary between subjects. Consequently, there will be no imputation for missing data.

Use the center ID in summaries and listings, as needed. Summary tables and listings will NOT generally be separated by investigator nor will investigator be a factor in any statistical models. Unless otherwise stated, all listings will be sorted by center ID, subject number, cohort, then by visit date.

Unless otherwise stated, continuous variables will be summarized with n, mean, median, standard deviation, minimum and maximum, and categorical variables will be summarized with frequency counts and percentages.

Summaries will be produced by cohort.

All laboratory data will be presented in GSK's standard units for reporting.

"Worst-case post-baseline" values will be derived using scheduled and unscheduled visits.

Planned times relative to study drug dosing will be used in all tables and summary figures.

Generally, only pre-specified planned times will be used in the summaries, statistical analyses and calculations of any derived parameters and unscheduled readings will be listed. However, both unscheduled and scheduled readings will be included in the computation of maximum toxicity and in post-baseline shifts displays for labs and in any listing.

Assessment windows will not be defined for the purpose of classifying measurements obtained outside scheduled assessment times.

Deviations from the analyses in the RAP will be identified in the CSR.

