## **9. DATA HANDLING CONVENTIONS**

### **9.1. Premature Withdrawal and Missing Data**

Because study treatment is dependent on the study endpoints (e.g., progression), the length of treatment for each subject will depend on the efficacy and toxicity of the treatment, so the duration of treatment will vary across subjects. Similarly the duration of follow up will also vary. All available time-to-event data will be analyzed using suitable statistical methods; subjects with shorter treatment and follow-up due to the natural history of their disease or medical necessities of the treatment of their disease will not be considered to have missing time-to-event data. For endpoints which determine the percentage of responders, subjects with unknown or missing best overall response will be assumed to be non-responders, and will be included in the denominator when calculating the percentages.

In the event that the study is terminated, all available data will be listed and a review carried out by the study team to assess which statistical analyses are still considered appropriate.

Missing data occurs when any requested data is not provided, leading to blank fields on the collection instrument. These data will be indicated by the use of a “blank” in subject listing displays. Answers such as “Not applicable” and “Not evaluable” are not considered to be missing data and should be displayed as such.

Subjects with the designation of treatment relationship for adverse events (AE)s and serious adverse events (SAEs) missing will have the worst case assumed to impute the relationship: if relationship to study treatment is missing it will be assumed to be “Yes”. There will be no other imputation for missing data other than what’s described in Section 9.2 for partial dates and for missing exposure end dates.

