### 9.2.4. Duration and Elapsed Time

Durations (e.g., the duration of an adverse event, duration of exposure, etc.) are calculated as the stop date minus the start date plus one.

For elapsed time (e.g., the time since initial diagnosis):

- If the reference date is on or after the event date, then the elapsed time is the reference date minus the event date + 1.
- If the reference date is before the event date then the elapsed time is the reference date minus the event date.

When reporting time to event (TTE) durations (progression-free survival, duration of intracranial, extracranial, and overall response, overall survival) in months, divide the number of days by 30.4375; to report in weeks divide the number of days by 7; to report in years divide the number of days by 365.25. These algorithms for time to event return decimal numbers, and ignore the actual numbers of days in the months or years between start date and stop date. The "year" used in these algorithms is 365.25 days long, and the "month" is one twelfth of that year.

For converting all other durations (e.g., duration of adverse events, duration of exposure, age) to weeks, months or years use the following:

- To report the duration in weeks, divide the number of days by 7.
- To report the duration in months use:  
 $(\text{YEAR}(\text{stopdate} + 1) - \text{YEAR}(\text{startdate})) * 12 + (\text{MONTH}(\text{stopdate} + 1) - \text{month}(\text{startdate}) - 1) + (\text{DAY}(\text{stopdate} + 1) >= \text{DAY}(\text{startdate}))$
- To report the duration in years use:

`intck('year', startdate, stopdate + 1) - (month(stopdate + 1) < month(startdate) or  
(month(stopdate + 1) = month(startdate) and day(stopdate + 1) < day(startdate)))`

The algorithms above for age and duration return whole numbers for months and years, accurately accounting for the actual numbers of days in the months or years between the start date and the stop date.

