**9.2.5. Imputation of Partial Dates**

Imputed partial dates will not be used to derive study day, duration (e.g., duration of adverse events), or elapsed time variables. In addition, imputed dates are not used for deriving the last contact date in overall survival analysis dataset.

With the exception of new anti-cancer start date on the Oncology time to event analysis dataset and exposure end date on the Exposure analysis dataset, imputed dates will also not be stored on datasets.

Imputed dates will not be displayed in listings. However, where necessary, display macros may impute dates as temporary variables for the purpose of sorting data in listings only. In addition partial dates may be imputed for specific analysis purposes as outlined below.

The partial date imputation will follow ADaM conventions. The ADaM approach is to populate the numeric date variables with the imputed date and add a flag variable to the dataset that indicates the level of imputation.

The flag variable can contain the values: blank, 'D', 'M', 'Y'.

blank: indicates that no imputation was done

D='Day': indicates that the day portion of the date is imputed

M='Month': indicates that the month and day portions of the date are imputed

Y='Year': indicates that the entire date (year, month, and day) is imputed

Example of Date Variables:

XYZD\_ - character date variable

XYZDT - numeric date variable

XYZDTFL - flag variable

Details on imputing partial dates for specific datasets follow.

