**Adverse Events (AE):**

Imputations in the adverse events dataset are used for slotting events to the appropriate study time periods and for sorting in data listings.

Dataset	Date	Missing Element	Rule

Dataset	Date	Missing Element	Rule
Adverse Events (AE)	Start Date	day, month, and year	
 
No Imputation for completely missing dates
 

		day, month	
 
If study treatment start date is missing (i.e. subject did not start study treatment), then set start date = January 1.
 
Else if study treatment start date is not missing:                             
 
If year of start date = year of study treatment start date then                                     
 
If stop date contains a full date and stop date is earlier than study treatment start date then set start date = January 1.
 
Else set start date = study treatment start date.
 
 
 
Else set start date = January 1.
 
 
 

		day	
 
If study treatment start date is missing (i.e. subject did not start study treatment), then set start date = 1st of month.
 
Else if study treatment start date is not missing:                             
 
If month and year of start date = month and year of study treatment start date then                                     
 
If stop date contains a full date and stop date is earlier than study treatment start date then set start date = 1st of month.
 
Else set start date = study treatment start date.
 
 
 
Else set start date = 1st of month.
 
 
 

	End Date		
 
No imputation for partial end dates will be performed
 

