
### **9.2.15. Cut-off date**

The analysis cut-off date for the primary analysis of study data will be established. The primary efficacy analysis will be performed when all subjects in cohort A have had the opportunity for three (3) post baseline disease assessments. All statistical analyses will be performed using all data collected in the database up to the data cutoff date. All data with an assessment date or event start date (e.g. vital sign assessment date or start date of an adverse event) prior to or on the cut-off date will be included in the analysis. Any data collected beyond the cut-off date will not be included in the analysis and will not be used for any derivations. All events with start date before or on the cut-off date and end date after the cut-off date will be reported as 'ongoing'. The same rule will be applied to events starting before or on the cut-off date and not having documented end date. This approach applies, in particular, to adverse event and concomitant medication reports.

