Summaries of the characteristics of each AE of special interest, including the number and percentage of subjects with these events will be provided for each separately. All summaries of AEs of special interest will use the number of subjects with the event as the denominator when calculating percentages. The summary of event characteristics will also be provided, including number of subjects with any event, number of events, number of subjects with any event that is serious, number of subjects with any event that is related to study treatment, the outcome of the event, maximum grade and the action taken for the event. The percentage will be calculated using the number of subjects with the event as the denominator. The worst case approach will be applied at subject level for the event outcome and maximum grade, i.e., a subject will only be counted once as the worst case from all the events experienced by the subject. For action taken in response to an event, subjects will be counted once under each action, e.g., if a subject has an event leading to both study treatment discontinuation and dose reduction, the subject will be counted once under both actions.

Summaries of onset for cutaneous squamous cell carcinoma including keratoacanthoma, and new primary melanomas (that is, AEs of special interest for which duration is not meaningful) will be produced. All other AEs of special interest will have summaries of the onset and duration produced.

In addition, subjects with each AE of special interest will be listed separately by AE of special interest.

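### As the SAP's date rules stand, the 17 AESI duration tables can use only events with complete start and stop dates on or before the cut-off, which tends to understate how long persistent events last

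*SAP*

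**What the plan says.** SAP 12.3 lists 20 AESIs. It asks for onset only for cutaneous squamous cell carcinoma (including keratoacanthoma) and new primary melanoma, and then says: "All other AEs of special interest will have summaries of the onset and duration produced". SAP 14.1 names the corresponding tables by first occurrence.

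The rules that decide which events can contribute a duration are spread over four sections:

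- SAP 9.2.4: "Durations (e.g., the duration of an adverse event, duration of exposure, etc.) are calculated as the stop date minus the start date plus one". Response duration, PFS and OS are grouped there as time-to-event durations; adverse event duration falls among the remaining ones.
- SAP 9.2.15: "All events with start date before or on the cut-off date and end date after the cut-off date will be reported as" 'ongoing'. Events with no documented end date are treated the same way. The section also says "Any data collected beyond the cut-off date will not be included in the analysis and will not be used for any derivations".
- SAP 9.2.5: "Imputed partial dates will not be used to derive study day, duration (e.g., duration of adverse events), or elapsed time variables". For adverse event end dates it adds "No imputation for partial end dates will be performed".
- SAP 9.1: "There will be no other imputation for missing data other than" what Section 9.2 sets out for partial dates and missing exposure end dates.

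The default for a continuous variable is in SAP 8: "continuous variables will be summarized with n, mean, median, standard deviation, minimum and maximum".

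**The concern.** An event that has not ended by the cut-off is likely to be one of the longer ones. If such events are dropped and ordinary summary statistics are taken over the rest, the result describes time to resolution among events that ended in time, while the table title promises the duration of the AESI. The pull is downward. It is weak for events that come and go quickly, such as pyrexia, and stronger for events that persist while treatment continues.

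Elsewhere the SAP deals with the same problem. Response duration uses Kaplan-Meier estimates with censoring (11.2), and open exposure records are closed at the earliest of data cut-off, study withdrawal or death (9.2.6). Nothing equivalent is written for adverse event duration.

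What is at stake is how clinicians read the persistence of toxicity. No efficacy or safety decision depends on it.

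**Working it through.** **Which events have a duration.** The SAP gives no figure for this point, so the check is to follow each kind of first occurrence through the rules.

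| First occurrence | Stop date usable? | Rule | Enters the duration statistics? |
|---|---|---|---|
| Complete start and stop dates, both on or before cut-off | Yes | 9.2.4 | Yes |
| Ends after the cut-off | No: later data barred, event reported as ongoing | 9.2.15 | No |
| No documented end date | No: reported as ongoing, no imputation available | 9.2.15, 9.1 | No |
| Partial start or end date | No: imputed partial dates barred from duration, partial end dates not imputed | 9.2.5 | No |

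The bar in 9.2.5 concerns partial dates. For an absent or post-cut-off end date, it is 9.1 and 9.2.15 that leave no value to use.

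**How many tables.** SAP 14.1 lists 17 first-occurrence onset-and-duration tables, from 3.1620 to 3.1668. This equals the 20 AESIs in 12.3 minus three onset-only tables (3.1611, 3.1614, 3.1617). The text of 12.3 alone would give 20 − 2 = 18; the difference is non-cutaneous malignancies, which 14.1 treats as onset only.

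**When it bites most.** SAP 14.1.1 delivers all displays at the primary analysis, which takes place once Cohort A has had the opportunity for three post-baseline assessments (SAP 4.2). On the Week 4, 8, 16 schedule, the last subject may have only about 16 weeks of follow-up, possibly still on treatment.

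**Size by rank, with no duration shape assumed.** Let n be first occurrences and k those still open, and suppose every open event would outlast the overall median. The median of the remaining events then has rank (n − k + 1)/2 instead of (n + 1)/2:

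- n = 15, k = 3: 13/2 = 6.5 instead of 16/2 = 8
- n = 30, k = 3: 28/2 = 14 instead of 31/2 = 15.5
- n = 30, k = 6: 25/2 = 12.5 instead of 31/2 = 15.5

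In large samples it sits at the (1 − f)/2 quantile of all events: the 47.5th percentile at f = 5% open, the 45th at 10% and the 40th at 20%. This is an upper bound on the rank shift. Under the shapes below with uniform follow-up, 76 to 92% of open events outlast the overall median.

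**Size under assumed shapes.** Monte Carlo with 1,000,000 draws per shape and follow-up set to give open fraction f. Entries are the percentage by which the median of completed events falls short, for uniform / fixed follow-up. All shapes and fractions are assumptions.

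| Shape | f = 5% | f = 10% | f = 20% |
|---|---|---|---|
| Exponential | 5.0 / 7.0 | 10.3 / 13.7 | 21.1 / 26.3 |
| Lognormal, sigma 1 | 4.4 / 6.1 | 8.7 / 11.8 | 17.4 / 22.4 |
| Weibull, shape 0.7 | 8.5 / 9.9 | 16.7 / 19.0 | 32.2 / 35.3 |
| Weibull, shape 1.5 | 2.6 / 4.7 | 5.4 / 9.3 | 11.7 / 18.4 |

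**Short against persistent events.** With exponential durations and time from onset to cut-off uniform over 365 days (again assumed), a true median of 14 days leaves 5.5% open and gives 13 days; 60 days leaves 23.3% open and gives 45; 180 days leaves 53.8% open and gives 77.

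**Would a censored median do better?** In 20,000 replicates (exponential, uniform follow-up, 20% open, no deaths), the typical estimate divided by the true median was, for Kaplan-Meier against completed events only: 0.99 against 0.83 with 5 events, 0.92 against 0.79 with 10, 1.01 against 0.79 with 15, and 1.00 against 0.79 with 30.

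**Death as a competing event.** Taking the predecessor study's 33.1-week median survival (Protocol 1.1.1) as a constant hazard, which is an assumption, death comes before resolution in 8%, 21% and 35% of events with mean duration 1, 3 and 6 months.

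**The case against.** The best reply is that the omission can be seen. Section 8 prints n, these are first-occurrence tables with at most one event per subject, and the characteristics tables in 12.3 give the number of subjects with the event. Subtracting duration n from that number gives the first occurrences without a duration. This stands as a limit on the concern. The difference does not, however, separate events ongoing at the cut-off from events open at death or events with partial dates. The outcome row does not help with that, because it takes each subject's worst case over all events.

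A second reply is that the dataset specifications, table shells and End of Study displays are separate documents (SAP 9.2, 14.1.1, 14.2) and may already show ongoing counts. That is possible and cannot be checked here.

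A third is that later follow-up closes most events. The End of Study analysis uses the cumulative safety data (SAP 4.2), and the protocol's amendment rationale reports only 9 patients still on treatment. Follow-up reduces the problem but need not remove it: Protocol 7.4.2.5 lets monitoring end at stabilization or loss to follow-up, and an event open at death never resolves.

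Three stronger readings are tempting and not supported:

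- That the SAP overlooks open events. It does not: 9.2.15 classifies them as ongoing. What is missing is how they enter a duration statistic.
- That the tables cover resolved events and nothing else is lost. Resolved events with partial dates drop out too, and the documents do not say whether a fatal event carries a stop date.
- That unresolved harm is hidden. The outcome rows and the AESI listings show it; only the duration statistics are affected.

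**Conclusion.** The concern holds as a minor point about descriptive safety tables. On the SAP's stated rules, the duration statistics in 17 tables rest on events with complete dates on or before the cut-off, and they tend to be too short for persistent AESIs, chiefly at the primary analysis.

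The size for this trial is unknown, because the documents do not give the fraction of events left out. The percentages in the working show direction and scale under assumed shapes; they are not estimates for this study. The conclusion assumes that the separate specifications add no rule that the SAP lacks. Duration is not part of the named safety endpoint, which is frequency and severity, and the primary analysis is untouched.

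**What to change.** In SAP 12.3, for each first-occurrence duration table:

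1. Show the number of first occurrences with complete dates, ongoing at cut-off or last contact, open at death, and with partial dates, so that the rows add up to all first occurrences.
2. Label the stop-minus-start statistics 'events with complete start and stop dates on or before cut-off'.
3. Where events suffice, mainly Cohort A or pooled cohorts, add a Kaplan-Meier median with ongoing events censored at the earliest of cut-off, last contact or death. Footnote that death is a competing event and that the median may not be estimable in small cohorts.

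If the shells already do steps 1 and 2, a cross-reference in 12.3 is enough for those two.

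Steps 1 and 2 cost a few table rows and a label, from data already held. Step 3 has a real but small cost. In the simulation at 20% open, the median could not be estimated in 4.6% of samples with 3 events, 1.9% with 5 and 0.1% with 10. Censoring at death also brings its own assumption, so the counts should come first.

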#### **12.4. Deaths and Serious Adverse Events**

Note that if any subject withdraws consent, no data after the date of withdrawing consent, including death, is supposed to appear in the database.

All deaths will be summarized based on the number and percentage of subjects. This summary will classify subjects by time of death relative to the last dose of medication (>30 days or ≤30 days). A supportive listing will be generated to provide subject-specific details on subjects who died.

All SAEs will be tabulated based on the number and percentage of subjects who experienced the event. Separate summaries will also be provided for dabrafenib- and trametinib-related SAEs, fatal SAEs and dabrafenib- and trametinib-related fatal SAEs. The summary tables will be displayed in descending order of total incidence by PT only.

A dabrafenib- or trametinib-related SAE is defined as an SAE for which the investigator classifies the relationship dabrafenib or trametinib as “Yes”. A worst case scenario approach will be taken to handle missing data, i.e. the summary table will include events with the relationship to study treatment as ‘Yes’ or missing.

SAEs are included in the listing of all adverse events. Separate supportive listings with subject-level details will be generated for

- Fatal SAEs
- Non-Fatal SAEs.

## 12.5. Adverse Events Leading to Discontinuation of Study Treatment and Dose Modifications

The following categories of AEs will be summarized separately in descending order of total incidence by PT only and separate supportive listings will be generated with subject level details for those subjects:

- AEs Leading to Discontinuation of Study Treatment
- AEs Leading to Dose Interruptions
- AEs Leadings to Dose Reductions

## 12.6. Pregnancies

While pregnancy itself is not considered to be an AE or SAE, any pregnancy complication or elective termination of a pregnancy for medical reasons will be recorded as an AE or SAE as described in the protocol. If subjects or subjects' partner become pregnant while on the study, the information will be included in the narratives and no separate table or listing will be produced.

## 12.7. Clinical Laboratory Evaluations

The assessment of laboratory toxicities will examine the following laboratory tests:

**Hematology:** White Blood Cell (WBC) count (absolute), Absolute Neutrophil Count (ANC), Hemoglobin (HGB), Hemoglobin A1C, Hematocrit (HCT), Platelet count, Basophils, Eosinphils, Lymphocytes, Monocytes, and Neutrophils. Basophils, Eosinphils, Lymphocytes, Monocytes, and Neutrophils are expressed as percentages. Note that hematocrit is not gradable by CTCAE v4.0.

**Clinical Chemistry:** Albumin, Gamma-Glutamyl Transpeptidase (GGT), Urea/Blood Urea Nitrogen (BUN), Calcium, Creatinine, Glucose, Lactate Dehydrogenase (LDH), Magnesium, Phosphate, Potassium, and Sodium. BUN and LDH are not gradable by CTCAE v4.0. For Sodium, Potassium, Calcium, and Glucose there will be two bi-directional parameters (hyper and hypo) created, and the tests will be graded by CTCAE v4.0 in both directions.

**Liver Function Tests:** Aspartateamino transferase (AST), Alanine aminotransferase (ALT), Alkaline phosphatase, and Total bilirubin (total). All these tests are gradable by CTCAE v4.0.

**Coagulation Tests:** Prothrombin time (PT) or International Normalized Ratio (INR), and activated partial thromboplastin time (APTT). INR and PTT are gradable by CTCAE v4.0 and PT is not. Coagulation tests are only done at baseline.

Laboratory grades will be reported using the Common Terminology Criteria for Adverse Events (CTCAE v4.0).

Summary of lab by scheduled visits using mean, median, standard deviation, minimum and maximum will be provided.

Summaries of worst case grade increase from baseline grade will be provided for all the lab tests that are gradable by CTCAE v4.0. These summaries will display the number and percentage of subjects with post-baseline grade increases from their baseline grade. Any increase in grade from baseline will be summarized along with any increase to a maximum grade of 3 and any increase to a maximum grade of 4. Missing baseline grade will be assumed as grade 0. In addition, the summary will include grade increase from baseline by scheduled visits and worst-case post-baseline. For laboratory tests that are graded for both low and high values, summaries will be done separately and labeled by direction, e.g., sodium will be summarized as hyponatremia and hypernatremia.

For lab tests that are not gradable by CTCAE v4.0, summaries of worst case changes from baseline with respect to normal range will be generated. Decreases to low, changes to normal or no changes from baseline, and increases to high will be summarized at each scheduled visit as well as for the worst case post-baseline. If a subject has a decrease to low and an increase to high during the same time interval, then the subject is counted in both the “Decrease to Low” categories and the “Increase to High” categories. In addition, the summary will include worst case changes from baseline with respect to normal range by scheduled visits.

Separate summary tables for hematology, chemistry, and liver function laboratory tests will be produced. Coagulation test results at baseline will be summarized.

A listing of selected laboratory tests and grades will be provided. A supporting listing of laboratory data for subjects with values outside the normal range will be provided. A separate listing of laboratory data with character values will also be provided.

Detailed derivation of baseline assessment is specified in Section 9.2.7.

Unless otherwise specified, the denominator in percentage calculation at each scheduled visit will be based on the number of subjects with non-missing value at each particular visit.

Coagulation tests only collected at baseline. Therefore these tests will not appear in any summaries of changes from baseline.

